5.1.3 Subject Exclusion Criteria

1. Uncontrolled concomitant disease.
2. Is currently participating and receiving study therapy or has participated in a study of an investigational agent and received study therapy or used an investigational device within 4 weeks of the first dose of treatment.
3. Has a diagnosis of immunodeficiency or is receiving systemic steroid therapy or any other form of immunosuppressive therapy within 7 days prior to the first dose of trial treatment. Use of inhaled or topical steroids or systemic corticosteroids < 10 mg/ day and prednisone equivalent ≤ 10 mg/d is permitted.
4. Has a known history of active TB (Bacillus Tuberculosis)

5. Hypersensitivity to pembrolizumab or any of its excipients.
6. Has had a prior anti-cancer monoclonal antibody (mAb) (excluding PD-1/PD-L1 inhibitor) within 4 weeks prior to study Day 1 or who has not recovered (i.e., \leq Grade 1 or at baseline) from adverse events due to agents administered more than 4 weeks earlier.
7. Has had prior chemotherapy, targeted small molecule therapy, or radiation therapy within 2 weeks prior to study Day 1 or who has not recovered (i.e., \leq Grade 1 or at baseline) from clinically significant adverse events due to a previously administered agent.
Note: Subjects with \leq Grade 2 neuropathy and \leq Grade 2 adrenal insufficiency are an exception to this criterion and may qualify for the study.
Note: If subject received major surgery, they must have recovered adequately from the toxicity and/or complications from the intervention prior to starting therapy.
8. Has a known additional malignancy that is progressing or requires active treatment. Exceptions include basal cell carcinoma of the skin or squamous cell carcinoma of the skin that has undergone potentially curative therapy or in situ cervical cancer.
9. Has known active central nervous system (CNS) metastases and/or carcinomatous meningitis. Subjects with previously treated brain metastases may participate provided they are stable (without evidence of progression by imaging for at least four weeks prior to the first dose of trial treatment and any neurologic symptoms have returned to baseline), have no evidence of new or enlarging brain metastases, and are not using steroids for at least 7 days prior to trial treatment. This exception does not include carcinomatous meningitis which is excluded regardless of clinical stability.
10. Has active autoimmune disease that has required systemic treatment in the past 2 years (i.e., with use of disease modifying agents, corticosteroids or immunosuppressive drugs). Replacement therapy (e.g., thyroxine, insulin, or physiologic corticosteroid replacement therapy for adrenal or pituitary insufficiency, etc.) is not considered a form of systemic treatment.
11. History of severe autoimmune disease.
12. Treatment with systemic immunostimulatory agents within 4 weeks or five half-lives of the drug, whichever is shorter, prior to enrollment (with the exception of checkpoint blockade therapy).
13. Treatment with systemic corticosteroids or other systemic immunosuppressive medications within past 4 weeks or 5 half-lives whichever is shorter. Use of inhaled or topical steroids or systemic corticosteroids < 10 mg/day and prednisone equivalent ≤ 10 mg/d is permitted.
14. Has a history of (non-infectious) pneumonitis that required steroids or current pneumonitis.
15. Has an active infection requiring systemic therapy.
16. Has a history or current evidence of any condition, therapy, or laboratory abnormality that might confound the results of the trial, interfere with the subject's participation for the full duration of the trial, or is not in the best interest of the subject to participate, in the opinion of the treating investigator.

17. Has known psychiatric or substance abuse disorders that would interfere with cooperation with the requirements of the trial.
18. Is pregnant or breastfeeding, or expecting to conceive or father children within the projected duration of the trial, starting with the pre-screening or screening visit through 120 days after the last dose of trial treatment.
19. Has a known history of Human Immunodeficiency Virus (HIV) (HIV 1/2 antibodies).
20. Has known active Hepatitis B (e.g., HBsAg reactive) or known Hepatitis C (e.g., HCV RNA [qualitative]).
21. Has received a live vaccine within 30 days of planned start of study therapy.

Note: Seasonal influenza vaccines for injection are generally inactivated flu vaccines and are allowed; however intranasal influenza vaccines (e.g., Flu-Mist®) are live attenuated vaccines, and are not allowed.

22. Patients unable to tolerate checkpoint inhibitor therapy.
23. Unresolved Grade 3 or any grade 4 non-hematological, treatment-related AEs attributed to prior PD-1/ PD-L1 checkpoint blockade. A minimum of 2 weeks from prior PD-1/PD-L1 checkpoint blockade to initiating study treatment.

5.2 Trial Treatments

This is a phase I/II study that will evaluate the safety and toxicity of this combinatorial approach. Eligible patients ≥ 18 years of age with histologically proven advanced solid malignancy or lymphoma who have failed PD-1 / PD-L1 checkpoint blockade therapy will be enrolled. Patients must have a candidate treatment lesion accessible and safe for radiotherapy and serial intralesional injections as specified by the protocol. They must also have at least one target lesion (distinct from treatment lesion and outside of treatment lesion radiation field) evaluable for response by RECIST.

This study will consist of a phase I dose escalation / de-escalation using a standard 3+3 design to determine safety and MTD of intralesional IL-2 which will be dose escalated in conjunction with standard fixed doses of RT and Pembrolizumab. The study will begin at dose level 3 and the dose will be de-escalated if needed to determine the MTD. At the MTD there will be a phase II dose expansion which will incorporate a simon-two stage design to assess efficacy and safety.

Patients will receive pembrolizumab and intralesional IL-2 in combination with hypofractionated radiotherapy.

- Radiotherapy will be delivered to the treatment lesion during the second cycle of therapy using an 8 Gy x 3 fractions palliative regimen. Fractions may be delivered on consecutive days or every other day but must be completed during weeks 1-2 of cycle 2 and will not be repeated in future cycles.
- Pembrolizumab will be delivered at 200 mg in three-week cycles .

- A total of four interleukin-2 treatments will be delivered into the treatment lesion by intralesional injection biweekly (at least 48 hours apart) starting 24-96 hours after the completion of radiotherapy and to be completed during the second on-trial cycle of Pembrolizumab. Intralesional injections will be performed by direct visualization and/or palpation of the lesion or under ultrasound or CT guidance as indicated. Intralesional IL-2 injections will follow guidelines which we have previously published [46]. IL-2 will be administered at three dose levels: 1) 3×10^6 IU, 2) 7×10^6 , 3) 15×10^6 IU. The study will begin at dose level 3 and the dose will be de-escalated as needed to establish the MTD.

At dose escalation levels 2 and 3 and in the phase II portion each patient will receive a test dose of 3×10^6 IU for their first injection prior to escalation to higher doses according to our published guidelines. For example, at dose level 3 each patient will receive an initial test dose of 3×10^6 IU of IL-2, which will be escalated to 7×10^6 for the second treatment and then 15×10^6 IU for the final two treatments as tolerated. If a dose level is not tolerated the treatment will be de-escalated to previous dose levels for subsequent treatments. If 3 million IU IL-2 is not tolerated the dose can be de-escalated to 1 million IU IL-2. If 1 million IU IL-2 is not tolerated the treatment will be deemed intolerable and patient removed from study (see Figure 6).

Patients will be assessed by a physician once during the first week of radiotherapy, weekly during intralesional IL-2 injections, and with every cycle of pembrolizumab. Routine laboratory evaluation will occur pre-treatment. For response assessment patient will have imaging pre-treatment and after every three cycles of Pembrolizumab. For collateral studies patients will undergo mandatory treatment lesion biopsies and blood draws pre-treatment and during the needle placement for the final IL-2 treatment.

Preliminary efficacy as determined by abscopal response rate, ORR, DCR and PFS will be assessed every 3 cycles. Patients on active treatment at 12 months may continue to receive pembrolizumab but will revert to standard of care (SOC) management and be labeled in “follow up”. At this time only PFS and long-term toxicity data will be collected every 3 months.

The primary endpoint is to determine if this regimen converts patients with resistance to PD-1/PD-L1 checkpoint blockade into responders as determined by abscopal response rate (defined as response rate at lesions not treated with RT + IL-2) using irRECIST as well as ORR, DCR, and PFS using RECIST 1.1. The secondary endpoint is tolerability, safety, and toxicity using CTCAE v4.03. Correlative studies include immunophenotyping serial tumor biopsies and blood samples.

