1.0 TRIAL SUMMARY

Abbreviated Title	A Phase I/II Study of Intralesional IL-2, Hypofractionated Radiotherapy, and Pembrolizumab in Patients Refractory to Standard-of-Care PD-1/PD-L1 Checkpoint Blockade
Trial Phase	I/II
Clinical Indication	Advanced solid malignancy or lymphoma. with progression on PD-1/L1 checkpoint inhibition.
Trial Type	Interventional
Route of administration	Pembrolizumab: intravenous IL-2: intratumoral injection Radiation: external beam
Trial Blinding	Unblinded, open-label
Treatment Groups	Phase I dose escalation of combination pembrolizumab, intralesional IL-2, and radiation in Advanced solid malignancy or lymphoma. Phase II dose expansion at MTD, which will incorporate a one-stage binomial design to assess efficacy and safety.
Number of trial subjects	25 maximum
Estimated enrollment period	28-36 months
Estimated duration of trial	4 years
Duration of Participation	28-36 months

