2.0 TRIAL DESIGN

Patients with advanced solid malignancies or lymphoma with progression on prior PD-1/L1 blockade will be enrolled. A total maximum of 25 patients will be enrolled.

Primary Objective: Abscopal response rate, ORR, DCR, PFS
Secondary Objective: Maximum tolerated dose (MTD), safety, and toxicity
Collateral Objectives: Immunophenotype serial tumor biopsies and blood samples

Phase I: IL-2 Dose Findin: 3+3 Design: (3-6 patient dose level, 6-18 patients total)				
	Treatment 1 dose	Treatment 2 dose	Treatment 3 dose	Treatment4 dose
Dose Level -1	1 x 10 ⁶ IU	1 x 10 ⁶ IU	1 x 10 ⁶ IU	1 x 10 ⁶ IU
Dose Level 1	3 x 10 ⁶ IU	3 x 10 ⁶ IU	3 x 10 ⁶ IU	3 x 10 ⁶ IU
Dose Level 2	3 x 10 ⁶ IU	7 x 10 ⁶ IU	7 x 10 ⁶ IU	7 x 10 ⁶ IU
Dose Level 3	3 x 10 ⁶ IU	7 x 10 ⁶ IU	15 x 10 ⁶ IU	15 x 10 ⁶ IU

Phase II: IL-2 Dose Expansion Binomial one-Stage Design (18 additional patients; analyzed with patients from MID)	

 P= 0.05, p1= 0.20, r1= 0, n1= 10, rTot=3, nTot=21, a= 0.1, power=0.8 Response will be assessed according to irRECIST and will be evaluated at the non-treatment lesions (abscopal response) 	

CT= computed tomography, DCR=disease control rate, MTD=maximum tolerated dose, ORR=objective response rate, PFS=progression free survival, RT=radiotherapy, P=pembrolizumab,

- a. Patients will be clinically evaluated prior to each cycle of pembrolizumab for the first 3 cycles and weekly during intralesional IL-2 injections, and thereafter every 3 cycles until off treatment.
- b. Laboratory evaluation will occur pre-treatment at every cycle.
- c. For response assessment, patient will have CT imaging pre-treatment and after every three cycles of pembrolizumab.

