8.4 All Study Variables

The panel of study endpoints and how they will be measured are described in the below table.

Table 14. Study Variables and Measurements

Endpoint	Variable	Measurement	Comment
Primary- Phase 1	ARR	irRECIST	Objective response at unirradiated sites, the endpoint for measuring responses for the Simon two-stage phase 2 study
Primary- Phase 1	ORR	RECIST and irRECIST	
Primary- Phase 1	DCR	RECIST and irRECIST	
Primary – Phase 1	PFS	RECIST and irRECIST	
Secondary- Phase 1	MTD	CTCAE V4.03	The maximum dose at which <2 of 6 patients experienced a DLT
Secondary- Phase 1	DLT	CTCAE V4.03	Outlined in section 5.4. A DLT is defined as \geq grade 4 injection site reaction OR \geq grade 3 treatment related immunologic adverse event (excluding injection site reactions) OR other \geq grade 3 treatment related adverse events that do not resolve to \leq grade 2 within 14 days of onset during the 30 day DLT period OR Grade 3 diarrhea, AST/ALT $>$ 3 x ULN with bilirubin $>$ 2 X ULN, or pneumonitis that requires holding treatment $>$ 14 days.
Secondary- Phase 2	Safety	CTCAE V4.03	
Translational	PBMC Immunophenotype	FACS	Blood
Translational	PBMC gene expression	qPCR	Blood
Translational	Systemic Cytokine Signature	Luminex	Serum
Translational	Tissue Immune Markers	IHC / IF	Tissue
Translational	Tumor gene expression	qPCR	Tissue
Translational	Mutational load	Whole exome sequencing/ RNA sequencing	Blood and Tissue
Translational	T cell receptor diversity	TCR deep sequencing	Blood and Tissue

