9.0 DATA AND STATISTICAL ANALYSIS PLAN

9.1 Sample Size

This is a phase I/II study that will enroll patients with an advanced solid malignancy, or lymphoma to determine if this regimen converts patients with resistance to PD-1/PD-L1 blockade into responders as determined by abscopal response rate (defined as response rate at lesions not treated with RT + IL-2) using irRECIST as well as ORR, DCR, and PFS using RECIST 1.1.

The phase I dose escalation will employ a standard 3 + 3 design with a goal of determining the MTD through DLT assessment. With three dose escalation levels this arm will recruit up to 18 patients.

The Phase II dose expansion will employ a binomial one stage design which will allow us to evaluate if this therapy can convert those resistant to PD-1/PD-L1 blockade into responders. Response will be assessed according to RECIST and will be evaluated at the non-treatment lesions (abscopal response). In order to minimize the required patient numbers, the 3 patients enrolled at the MTD will be included in the phase II efficacy evaluation. We have chosen a threshold of 5% response as not worthy of further evaluation (p0) and a threshold of 20% as worthy of further evaluation in a larger trial (p1). The trial will enroll a total of 21 patients including the three patients treated at the MTD in the phase I (ntot) and must have greater than 3 responders (rtot) for this regimen to be deemed worthy of further evaluation. This design provides a type I error rate of 0.1 and power of 0.82. This trial design will enroll a total maximum of 25 evaluable patients

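### Phase II is labelled one-stage in 1.0, 2.0 and 9.1 but Simon two-stage in 5.2 and Table 14, and the stated power of 0.82 fits only a one-stage test passed with at least 3 of 21 responders

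*Combined protocol and SAP*

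**What the plan says.** Three places describe a single-stage test. Section 1.0: "Phase II dose expansion at MTD, which will incorporate a one-stage binomial design to assess efficacy and safety". The phase II box in 2.0 is headed: "Phase II: IL-2 Dose Expansion Binomial one-Stage Design (18 additional patients; analyzed with patients from MID". Section 9.1: "The Phase II dose expansion will employ a binomial one stage design".

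Two places describe a two-stage test. Section 5.2: "At the MTD there will be a phase II dose expansion which will incorporate a simon-two stage design to assess efficacy and safety". Table 14 in 8.4, commenting on the abscopal response rate: "the endpoint for measuring responses for the Simon two-stage phase 2 study".

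Section 2.0 is itself mixed. Under its one-stage heading it gives "P= 0.05, p1= 0.20, r1= 0, n1= 10, rTot=3, nTot=21, a= 0.1, power=0.8", where r1 and n1 are first-stage quantities.

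Section 9.1 sets the null rate at 5%, the target rate at 20% and the total at 21, including three patients from the phase I MTD cohort. Its success rule is that the trial "must have greater than 3 responders (rtot) for this regimen to be deemed worthy of further evaluation". It states a type I error of 0.1 and power of 0.82 and mentions no interim look. Section 5.10, on early termination, has no criterion based on response. No section says which text governs.

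**The concern.** A one-stage trial enrols 21 patients whatever the early responses. A Simon two-stage trial can stop for futility part-way. If the regimen is inactive, the two labels would often lead to different conduct, and the type I error and power differ between them. The trial is open-label, so a look that is named but not written could be invoked, or not, after the responses are known.

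A second ambiguity sits in the same sentences. The success cut-off printed in 9.1 does not produce the power printed beside it. Exactly 3 responders of 21 is a failure under the printed rule and a success under the rule that yields 0.82.

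**Working it through.** **Inputs.** p0 = 0.05, p1 = 0.20 and n = 21 (9.1; also 2.0); r1 = 0 and n1 = 10 (2.0 only); stated type I error 0.1 (2.0 and 9.1); stated power 0.8 (2.0) and 0.82 (9.1). All tests are one-sided exact binomial.

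**1. Reproduce the stated power: one stage, success at 3 or more.** P(X ≥ 3) = 1 − P(0) − P(1) − P(2), with X ~ Bin(21, p).
- p = 0.05: 1 − 0.3406 − 0.3764 − 0.1981 = 0.0849.
- p = 0.20: 1 − 0.0092 − 0.0484 − 0.1211 = 0.8213.

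This matches 0.82, and the stated 0.1 holds as a ceiling. A search over n shows that 21 is the smallest one-stage size with type I error at most 0.10 and power at least 0.80.

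**2. Printed rule: one stage, more than 3 (4 or more).** Subtract P(X = 3).
- p = 0.05: 0.0849 − 0.0660 = 0.0189.
- p = 0.20: 0.8213 − 0.1917 = 0.6296.

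**3. Add the inferred stop at 0 of 10.** The stop removes those successes in which the first 10 patients give no responders and the last 11 give enough alone. The loss is P(0 of 10) × P(Y ≥ R), with Y ~ Bin(11, p) and R the cut-off.
- P(0 of 10) = 0.95^10 = 0.599 at 5%; 0.80^10 = 0.107 at 20%.
- R = 3, p = 0.05: 0.0849 − 0.5987 × 0.0152 = 0.0758.
- R = 3, p = 0.20: 0.8213 − 0.1074 × 0.3826 = 0.7802.
- R = 4, p = 0.05: 0.0189 − 0.5987 × 0.00155 = 0.0180.
- R = 4, p = 0.20: 0.6296 − 0.1074 × 0.1611 = 0.6123.

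**4. Expected size with the stop.** 10 + 11 × (1 − 0.599) = 14.4 at 5%, and 10 + 11 × (1 − 0.107) = 19.8 at 20%, against a fixed 21.

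| Design | Cut-off | Type I error | Power |
|---|---|---|---|
| One-stage | ≥ 3 of 21 | 0.085 | 0.821 |
| Stop at 0/10 | ≥ 3 of 21 | 0.076 | 0.780 |
| One-stage | > 3 of 21 (printed) | 0.019 | 0.630 |
| Stop at 0/10 | > 3 of 21 (printed) | 0.018 | 0.612 |

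**5. Do the 2.0 parameters form a standard Simon design?** For 5% versus 20%, type I error 0.10 and power 0.80, the search gives an optimal design with first stage 0/9 and 24 in total, and a minimax design with first stage 0/12 and 21 in total; both need at least 3 responders. The listed 0/10 first stage is neither.

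**The case against.** Three stronger readings are tempting, and the documents support none of them.

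- **A team following 5.2 would stop after 0 of 10.** Section 5.2 gives no stage size, boundary or interim action. The numbers stand only in 2.0, under a one-stage heading. The stop is an inference from two sections, not a written competing rule.
- **The error rates are undefined.** Section 9.1, the sample-size section, names one design and states its type I error and power. The summary and the design section carry the same label. The two outliers are a sentence under trial treatments and a table comment in the correlative-science section, neither with operating characteristics. What is missing is a statement that 9.1 governs.
- **Both stated powers rule out the two-stage design.** Only the 0.82 does. The 0.8 in 2.0 has one decimal, and 0.780 rounds to it.

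It is also fair to say that with the cut-off at 3 the two designs differ modestly (power 0.821 against 0.780, both type I errors under 0.1), that the fall to 0.63 comes from the cut-off and not the label, and that 9.4 treats all results as preliminary. All of this stands. It limits the size of the point but does not remove the conflict: the two-stage text is current, and nothing in the document overrides it.

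**Conclusion.** This is an internal inconsistency in current text, and it needs correcting. The label conflict leaves open whether there is an interim look. If the 0-of-10 stop were applied, it would trigger with probability 0.60 at the 5% rate and 0.11 at 20%, and power would fall by about 4 points, from 0.821 to 0.780. The larger effect is the printed cut-off, which lowers power to 0.630 without the stop and 0.612 with it.

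The stated power of 0.82 supports one-stage with at least 3 of 21 as the intended design, because no other combination above reproduces it. That is an inference about intent. If rTot = 3 is read like r1 = 0, as the largest failing count, it agrees with the printed rule, so the sponsor has to confirm the cut-off as well as the label.

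The figures assume 21 evaluable patients, independent responses at a common rate and, for the two-stage values, that r1 = 0 and n1 = 10 mean stopping when none of the first 10 patients responds.

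**What to change.** The sponsor should first confirm the design.

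**If one-stage, which the stated power supports:** replace the Simon wording in 5.2 and Table 14; delete r1 and n1 from 2.0 and align its rTot and power with 9.1; and write the 9.1 rule as at least 3 responders of 21, with exact type I error 0.085 and power 0.82.

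**If the look after 10 patients is wanted:** write the interim rule in every section that describes phase II, say whether the three phase I MTD patients count among the first 10, and restate type I error as 0.076 and power as 0.78, with success at 3 or more.

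Keeping the cut-off at more than 3 would mean stating power of 0.63 (0.61 with the look). Reaching 80% power with that cut-off needs 27 patients in one stage (type I error 0.044, power 0.818), above the stated maximum of 25.

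Either of the first two options costs wording in about four places and no extra patients.

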5.2.1 Trial Procedures

Patients will be recruited from the UC Davis Comprehensive Cancer Center (UCDCCC). All patients will be registered at the UC Davis facility. Patients will be identified through the various clinics at UC Davis, at the UC Davis multidisciplinary tumor boards, and the UCDCCC Phase I clinic. Coordinated recruitment efforts specifically tailored for this trial will be created. We conservatively project a 36-month accrual period.

5.2.2 Treatment Plan

Table 3. Treatment Plan

Agent	Dose	Route	Frequency
IL-2	Dose 1: 3×10^6 IU Dose 2: 7×10^6 IU Doses 3 & 4: 15×10^6 IU	Intratumoral	
• 4 total doses• Starting 24–72 hours after the completion of radiotherapy and• Completed during Cycle 2 of pembrolizumab• Does not repeat with future cycles
Radiation	24 Gy	External beam	
• 3 fractions of 8 Gy palliative regimen• Delivered 12–96 hours apart• Must be completed during week 1 of Cycle 2• Does not repeat with future cycles.
Pembrolizumab	200 mg	IV	Q 3 weeks (one cycle)

Eligible patients with advanced solid malignancies or lymphoma who fail to respond to or progress on PD1/PDL1 checkpoint blockade will be enrolled. Patients will receive pembrolizumab and intralesional IL-2 in combination with hypofractionated radiotherapy.

5.2.2.1 Radiotherapy

Radiotherapy will be delivered to the treatment lesion during the first week of Cycle 2 using an 8 Gy x 3 fractions palliative regimen. Fractions may be delivered on consecutive or every other day but must be completed during week 1-2 of Cycle 2 and will not be repeated in future cycles.

